3.2.3 Treatment Duration

The maximum duration of treatment will be 5 days; however, IMP treatment may be ended at a treatment period of shorter than 5 days at the discretion of the investigator or subinvestigator, if either of the following criteria is met:

- All congestive symptoms are resolved and no further improvement in volume overload is necessary.
- The subject becomes capable of fluid management by oral intake alone.

[Rationale for the treatment duration]

The maximum treatment duration in this trial is 5 days, which is the same as that in the phase 3 confirmatory trial (Trial 263-102-00003).

If all congestive symptoms disappear and further improvement in volume overload is judged unnecessary by the investigator or subinvestigator, IMP treatment will be ended because no additional diuretic treatment is required. In addition, if fluid control by oral intake alone is attained during the treatment period, IMP treatment will be ended because the subject is judged to have recovered from difficulty in or incapability of oral intake.

3.3 Trial Population

3.3.1 Number of Subjects and Description of Population

The trial population will comprise a total of 40 Japanese male and female CHF patients aged 20 to 85, inclusive, with volume overload despite having received injection diuretics other than vasopressin antagonists and who have difficulty with or are incapable of oral intake and who are capable of being hospitalized from the time of informed consent until the end of the treatment period.

3.3.2 Subject Selection and Numbering

All subjects will be given a unique subject identifier (ID; site number [3 digits] + subject number ['S' + 5 digits]) upon providing consent. The site number will be designated by the sponsor. The subject number will be given in the order of informed consent from S00001 as the serial numbers in the trial sites. The trial site will prepare a list connecting all subjects consenting to participation in the trial and their subject identifiers, and retain the list.

3.4 Eligibility Criteria

3.4.1 Informed Consent

Informed consent will be freely obtained from all subjects. The informed consent form (ICF) will be approved by the same institutional review board (IRB) that approves this protocol.

Each written information and ICF will comply with the ICH (International Conference on Harmonisation) Good Clinical Practice (GCP) Guideline⁸ and local regulatory requirements.

Investigators or subinvestigators may discuss trial availability and the possibility for entry with a potential subject without first obtaining consent. However, informed consent must be obtained and documented prior to initiation of any procedures that are performed solely for the purpose of determining eligibility for research, including withdrawal from current medication(s).

Potential subjects are free to refuse entry into the trial, or withdraw from the trial at any time, without justification, and there will be no consequences to their further care.

Once the appropriate essential information has been provided and fully explained in layman's language to the subject by the investigator or subinvestigator, the IRB-approved written ICF will be signed and dated by both the subject and the person obtaining consent (investigator or subinvestigator), as well as by the trial coordinator, if he/she provides supplemental explanation. If the subject is able to consent but unable to sign the ICF for physical or therapeutic reasons, a witness should be present with the subject during the course of informed consent. To prove that the subject has been fully informed and has expressed his/her voluntary consent, the witness must sign and date the ICF, and write the name of the subject, the reason(s) that the subject is not able to personally sign the ICF, and the relationship between the subject and the witness in the margin of the ICF, while the signature section of the ICF should be left blank. The witness should be a person who

is independent of the trial and who cannot be unfairly influenced by persons involved with the trial. The subject will receive a copy of the written information and the signed ICF; the original shall be kept on file by the investigator or subinvestigator.

Subjects, as well as their witnesses (if applicable), may be asked to sign additional ICFs if the protocol is amended and the changes to the protocol result in additional information that needs to be provided to the subjects, so that they can make a knowledgeable and voluntary decision on trial participation.

Deoxyribonucleic acid (DNA) storage is optional. Subjects who do not consent to DNA storage may participate in the trial.

Subjects must agree to restrictions to concomitant medications as described in [Section 4.1](#).

Subjects who have consented to participation in the trial, but who does not receive IMP are permitted to be re-screened once. In the event that the screening examination is repeated, a new ICF signed by the subject must be obtained and a new subject identifier will be assigned to the subject (see [Section 3.9](#)).

3.4.2 Inclusion Criteria

Subjects must meet all of the inclusion criteria in [Table 3.4.2-1](#).

Table 3.4.2-1 Inclusion Criteria	
1	Patients receiving loop diuretic injection at a dose equivalent to furosemide 20 mg/day or higher
2	CHF patients in whom lower limb edema, pulmonary congestion, and/or jugular venous distension due to volume overload is present
3	Male or female patients age 20 to 85, inclusive, at time of informed consent
4	Patients who are judged by the investigator or subinvestigator to have difficulty or be incapable of oral intake, including patients who are judged by the investigator or subinvestigator to require nothing by mouth (NPO) management
5	Patients who are currently hospitalized or who are capable of being hospitalized from the time of informed consent until the end of the treatment period
6	Patients who are capable of giving informed consent

[Rationale for the inclusion criteria]

- 1 This criterion is set to enroll patients who have volume overload despite having received diuretics other than vasopressin antagonists.
- 2 Volume overload may be manifested by lower limb edema, pulmonary congestion, jugular venous distension, hepatomegaly, and cardiac third sound. Among these manifestations, lower limb edema, pulmonary congestion, and jugular venous distension are selected for the inclusion criterion, because these symptoms are

hardly affected by other factors and were reported by many subjects in a phase 3 trial of tolvaptan (Trial 156-06-002) and a phase 2 trial (Trial 263-102-00001) of OPC-61815 in patients with CHF.

- 3 Subjects at lower limit of age 20 years are legal adults in Japan and therefore capable of being responsible for their consent. The upper age limit is set at 85 years because many patients with CHF are elderly and also based on safety considerations.
- 4 This criterion is set to evaluate the safety of OPC-61815 in patients who have difficulty with or are incapable of oral intake.
- 5 This criterion is set to appropriately evaluate the safety of the IMP.
- 6 The criterion is set to ensure the ethically appropriate implementation of the trial.

3.4.3 Exclusion Criteria

Subjects will be excluded if they meet any of the exclusion criteria in [Table 3.4.3-1](#).

Table 3.4.3-1 Exclusion Criteria	
1	Patients who are on a ventricular assist device
2	Patients who have any of the following diseases, complications, or conditions: 
 • Suspected hypovolemia • Hypertrophic cardiomyopathy (excluding dilated phase) • Valvular disease with significant valvular stenosis • Hepatic encephalopathy with difficulty in adequate fluid intake
3	Patients who have experienced acute myocardial infarction within 30 days prior to the screening examination
4	Patients with a definite diagnosis of active myocarditis or amyloid cardiomyopathy
5	Patients who have any of the following medical histories: 
 • History of sustained ventricular tachycardia or ventricular fibrillation within 30 days prior to the screening examination (for patients without an implantable cardioverter defibrillator) • History of cerebrovascular disease (excluding asymptomatic cerebral infarction) within 6 months prior to the screening examination • History of hypersensitivity or idiosyncratic reaction to benzazepines or benzazepine derivatives such as the ingredients of OPC-61815, tolvaptan, mozavaptan hydrochloride, and benazepril hydrochloride
6	Patients who have any of the following diseases, complications, or conditions: 
 • Poorly controlled diabetes mellitus • Anuria • Dysuria associated with urinary tract obstruction, calculus, or tumor
7	Patients with supine systolic blood pressure of <90 mmHg
8	Patients with any of the following abnormalities in laboratory test results: 
 • Total bilirubin: >3.0 mg/dL • Serum or plasma creatinine: >3.0 mg/dL • Serum or plasma sodium concentration: <125 mEq/L

Table 3.4.3-1 Exclusion Criteria

	
 • Serum or plasma sodium concentration: >147 mEq/L • Serum or plasma potassium concentration: >5.5 mEq/L
9	Patients with current symptoms or a history of hepatic impairment (including patients with aspartate aminotransferase [AST] or alanine aminotransferase [ALT] exceeding 3 times the upper limit of the reference range at the screening examination)
10	Patients who have undergone open-heart surgery (eg, open-heart surgery for valvular disease, coronary bypass surgery, or surgery in thoracic aorta) within 30 days prior to the screening examination
11	Patients who have difficulty with spontaneous respiration or who have been on tracheal intubation under sedative therapy
12	Patients with severe disturbed consciousness (ie, coma or stupor)
13	Women who are breast-feeding or who have a positive pregnancy test result prior to receiving IMP
14	Sexually active men or women of childbearing potential (WOCBP) who do not agree to practice birth control or remain abstinent during the trial and for 30 days after the final IMP administration ^a
15	Patients who are otherwise judged to be ineligible by the investigator or subinvestigator

^aNonchildbearing potential is defined as male and female subjects who are surgically sterile (ie, male subjects who have undergone bilateral orchidectomy and female subjects who have undergone bilateral oophorectomy and/or hysterectomy) and female subjects who have been postmenopausal for at least 12 consecutive months.

[Rationale for the exclusion criteria]

- 1 This criterion is set because the use of a ventricular assist device may affect the safety evaluation of the IMP and with a view toward subject safety.
- 2 Excessive diuretic treatment may adversely affect these symptoms.
- 3 to 9 These criteria are based on safety considerations.
- 10 This criterion is set because the safety, efficacy, and pharmacodynamics of the IMP could not be appropriately evaluated in such patients.
- 11, 12 These criteria are based on safety considerations.
- 13 to 15 These criteria are based on general safety and ethical considerations.

3.5 Endpoints

3.5.1 Safety Endpoints

Adverse events, clinical laboratory tests, physical examination, vital signs (blood pressure, pulse rate, and body temperature), and 12-lead electrocardiogram (ECG)

[Rationale for the safety endpoints]

Adverse events, clinical laboratory tests, physical examination, vital signs (blood pressure, pulse rate, and body temperature), and 12-lead ECG are commonly used as endpoints of general safety.

3.5.2 Pharmacodynamic Endpoints

Urine volume, fluid intake, fluid balance, serum sodium concentration, serum potassium concentration, serum osmolality, urine sodium excretion, urine potassium excretion, urine osmolality, and biomarkers (plasma concentrations of AVP and brain natriuretic peptide [BNP], plasma renin activity, and serum concentrations of N-terminal pro BNP [NT-proBNP] and troponin I)

[Rationale for the pharmacodynamic endpoints]

Urine volume, urine osmolality, urine sodium excretion, urine potassium excretion, serum osmolality, serum sodium concentration, and serum potassium concentration are selected as endpoints to evaluate the aquaretic effect of OPC-61815. Fluid intake and fluid balance are selected to evaluate the impact of aquaresis by OPC-61815 on fluid balance. Tolvaptan, which is the active ingredient of OPC-61815, is an AVP V₂-receptor antagonist; therefore, plasma AVP concentration is selected to evaluate the effects on plasma AVP concentration. Plasma renin activity is selected to evaluate the impact of aquaresis by OPC-61815 on the renin-angiotensin system. The plasma concentrations of BNP, serum concentrations of NT-proBNP and troponin I are selected to evaluate the impact of the aquaretic effect of OPC-61815 on cardiac function.

3.5.3 Efficacy Endpoints

- Body weight
- Congestive symptoms

Lower limb edema, jugular venous distension, hepatomegaly, pulmonary rales, cardiac third sound, cardiothoracic ratio, and pulmonary congestion

- Dyspnea

Respiratory rate, paroxysmal nocturnal dyspnea, orthopnea, and subject-assessed dyspnea

- New York Heart Association (NYHA) classification

[Rationale for the efficacy endpoints]

Body weight is selected as a measure that objectively reflects the general state of volume overload. Congestive symptoms and dyspnea are selected as symptoms or findings that reflect the volume overload state in patients with CHF. NYHA classification is selected as a measure that assesses subjective physical activity in patients with CHF.

3.6 Measures to Minimize/Avoid Bias

This trial is an uncontrolled trial.

3.7 Trial Procedures

Trial assessment time points are summarized in [Table 3.7-1](#).

Serum sodium and potassium concentrations during the treatment period will be measured at both the central laboratory (central measurement) and the trial site (local measurement). If serum sodium and potassium concentration measurement is difficult to perform at the trial site, plasma sodium and potassium concentrations may be measured. Either serum or plasma should be used consistently for measurement of sodium and potassium concentrations in a given subject. However, serum sodium and potassium concentrations will be measured at the central laboratory. Clinical laboratory tests will be conducted at each trial site for the screening examination, and at the central laboratory from Day 1 onward.

Table 3.7-1 Schedule of Assessments

Item	Day	Screening	Treatment Period					Follow-up
		Day -1 to Predose of Day 1	1	2	3	4	5	
Informed consent		♦						
Informed consent for DNA storage		○						
Subject background		♦						
Inclusion/exclusion criteria		♦	●					
Confirmation of concomitant medication/therapy			←→					
Subject registration		♦						
Hospitalization			←→					
IMP administration			X	X	X	X	X	
Administration of diuretic agents			X	X	X	X	X	X
Dose escalation ^a				●	●			
Confirmation of IMP compliance			♦	♦	♦	♦	♦	
Cumulative urine volume ^b			←→←→←→←→←→					
Urine volume, fluid intake ^b			←→←→←→←→←→					
Urine sodium and potassium concentrations, urine osmolality ^c			←→←→←→←→←→					
Serum sodium ^d and potassium concentrations ^d		♦	● ^e ■	● ^e ■ ^f	●■ ^f	●	●	♦
Serum osmolality			●■	●■ ^f	●■ ^f	●	●	♦
Body weight		♦	● ^e	●	●	●	●	♦
Dyspnea ^g		♦	♦	♦	♦	♦	♦	

Table 3.7-1 Schedule of Assessments

Item	Day	Screening	Treatment Period					Follow-up
		Day -1 to Predose of Day 1	1	2	3	4	5	Day 6/ At Withdrawal (Day After Final IMP Administration)
Congestive symptoms ^h		♦	♦	♦	♦	♦	♦	♦
Chest x-ray (cardiothoracic ratio, pulmonary congestion) ⁱ		♦	●				♦	
Adverse events		←						→
Laboratory tests		♦ ^j	●				♦	♦
Physical examination		♦	♦	♦	♦	♦	♦	♦
Vital signs (blood pressure, pulse rate, body temperature)		♦	● ^e ■	● ■ ^f	● ■ ^f	●	●	♦
12-Lead ECG ^k			● ■		♦			♦
NYHA classification		♦						♦
Biomarkers ^l			●					♦
Urine pregnancy test (WOCBP only)		♦						♦
Blood sampling for DNA storage ^m			○					
Adjustment of infusion solution ⁿ			←					→

X = Time of drug administration should not be markedly different on each day; ● = Before start of IMP administration; ■ = For measurements on Day 1 and the day of dose escalation assessment, see the corresponding time points after start of IMP administration as specified in [Section 3.7.1.2](#) and [Section 3.7.1.5](#); ♦ = At a feasible time (on Day 1, at a feasible time after start of IMP administration); ○ = Optional (subjects at sites with a DNA storage agreement who have given informed consent for DNA storage prior to start of the trial)

^aDose escalation assessment: Required on Day 2, performed on Day 3 if applicable

^bMeasurements of cumulative urine volume, urine volume, and fluid intake (with oral intake and intake via transfusions, nasogastric feeding tubes, and gastronomy tubes): Time intervals for measurement of cumulative urine volume ([Table 3.7.5.1-1](#)) and urine volume ([Table 3.7.5.1-2](#)) are set on Day 1

and the day of dose escalation. Cumulative urine volume and urine volume will be measured for each time interval as specified in [Section 3.7.1.2](#) and [Section 3.7.1.5](#). From Days 2 onwards, except the day of dose escalation, cumulative urine will be collected for 24 hours from the time of complete urination at predose and daily urine volume and fluid intake will be measured for that time interval.

^cUrine sodium and potassium concentrations, and urine osmolality: Urine samples collected at each cumulative urine collection time interval as shown in [Table 3.7.5.1.1-1](#) will be centrally measured by the contract research organization for clinical laboratory tests (central laboratory).

^dSerum sodium and potassium concentrations: Measured both at the central laboratory and at the trial site for appropriate fluid management. If serum sodium and potassium concentration measurement is difficult to perform at the trial site, plasma sodium and potassium concentrations may be measured. Either serum or plasma samples should be used consistently for measurement of sodium and potassium concentrations in a given subject. However, serum sodium and potassium concentrations will be measured in the central laboratory. (At screening, serum or plasma sodium and potassium concentrations will be measured only at the trial site.)

^eSerum sodium concentration (local measurement), serum potassium concentration (local measurement), body weight, chest x-ray, and vital signs (blood pressure, pulse rate, and body temperature): If measurements are performed on Day 1 as part of the screening examination, the measurements do not have to be repeated at predose on Day 1.

^fPerformed on the day that the dose is increased to 16 mg.

^gDyspnea: Respiratory rate, paroxysmal nocturnal dyspnea, orthopnea, and subject-assessed dyspnea (assessment of presence or absence of symptoms by subjects at screening)

^hCongestive symptom findings: Lower limb edema, hepatomegaly, jugular venous distension, pulmonary rales, and cardiac third sound

ⁱChest x-ray: Chest x-ray does not have to be repeated if it has been performed within 24 hours before informed consent. The results of chest x-ray performed prior to the acquisition of informed consent can be used to determine eligibility of the subject to participate in the trial.

^jLaboratory tests: At screening, laboratory tests are performed at the trial site.

^k If the serum potassium is confirmed to exceed 5.5 mEq/L at the trial site or the central laboratory at any time point in the period with no specified 12-lead ECG, a 12-lead ECG will be performed as an unscheduled examination.

^lPlasma concentrations of AVP and BNP, plasma renin activity, and serum concentrations of NT-proBNP and troponin I

^mDNA storage: In principle, blood sampling for DNA storage will be performed at predose on the day of initial IMP administration (Day 1). Informed consent for DNA storage must be obtained by the blood sampling for DNA storage. If blood sampling is not performed at that time or needs to be repeated, blood sampling will be performed at a feasible time during the trial period.

ⁿThe infusion solution will be checked and adjusted according to the specifications for each day (see [Section 3.7.1.2](#) to [Section 3.7.1.6](#)).

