3.2.2 Dose Escalation Decision

1) Predose on Day 2

When all (No. 1 to No. 4) of the Day 2 dose escalation criteria ([Table 3.2.2-1](#)) are met, the dose will be increased to 16 mg.

When any of the following criteria are not met, the dose for Day 2 and onward will remain at 8 mg, and dose escalation assessment will not be repeated at predose on Day 3.

- No. 1 of the Day 2 dose escalation criteria
- No. 3 of the Day 2 dose escalation criteria
- No. 4 of the Day 2 dose escalation criteria

Table 3.2.2-1 Day 2 Dose Escalation Criteria	
1	An adequate response is absent (when either of the following is met). 
 1) When the increase in daily urine volume from baseline (the daily urine volume through immediately predose on Day 1) is ≤ 500 mL: Any congestive symptom (lower limb edema, hepatomegaly, jugular venous distension, cardiothoracic ratio, pulmonary rales, or cardiac third sound) is present. 2) When the increase in daily urine volume from baseline (the daily urine volume through immediately predose on Day 1) is > 500 mL or cannot definitely be concluded to be ≤ 500 mL: Body weight did not decrease as compared with predose on Day 1 with no improvement in congestive symptoms.
2	The serum sodium concentration at predose on Day 2 is ≤ 147 mEq/L. ^a
3	An increase of > 10 mEq/L in serum sodium concentration is not evident within 24 hours after start of IMP administration on Day 1. ^a
4	No safety concerns have arisen since the start of IMP administration on Day 1 at the discretion of the investigator or subinvestigator.

^aIf serum sodium concentration measurement is difficult to perform at the trial site, plasma sodium concentrations will be used for the assessment.

2) Predose on Day 3

When only No. 2 of the Day 2 dose escalation criteria was not met, eligibility for dose escalation will be reassessed on Day 3 according to the Day 3 dose escalation criteria ([Table 3.2.2-2](#)).

When all (No. 1 to No. 4) of the Day 3 dose escalation criteria are met, the dose will be increased to 16 mg. When any of the Day 3 dose escalation criteria are not met, the dose for Day 3 onward will remain at 8 mg.

Table 3.2.2-2 Day 3 Dose Escalation Criteria

1	An adequate response is absent. 1) Body weight did not decrease as compared with predose on Day 2 with no improvement in congestive symptoms.
2	The serum sodium concentration at predose on Day 3 is ≤ 147 mEq/L. ^a

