	6 to 8 hours after start of IMP administration	+4 hours ^a
	8 hours after start of IMP administration to immediately before start of IMP administration on the next day	
Urine sampling for the measurement of urine sodium concentration, urine potassium concentration, and urine osmolality	At the end of each urine collection interval shown in Table 3.7.1.2-1	
12-Lead ECG	1 hour after start of IMP administration	+1 hour
Vital signs (blood pressure, pulse rate, and body temperature)	1 hour after start of IMP administration	+1 hour
	4 hours after start of IMP administration	+1 hour
	8 hours after start of IMP administration	+4 hours
Serum osmolality, serum sodium concentration, and serum potassium concentration (Serum sodium and potassium concentrations will be measured also at the trial site.)	4 hours after start of IMP administration	+1 hour
	8 hours after start of IMP administration	+4 hours

^aAllowable time window for the end of each interval

6) At a feasible time after start of IMP administration

- Dyspnea (respiratory rate, paroxysmal nocturnal dyspnea, orthopnea, and subject-assessed dyspnea)
- Congestive symptoms (lower limb edema, hepatomegaly, jugular venous distension, pulmonary rales, and cardiac third sound)
- Physical examination
- Adverse Events
- Concomitant medications and therapies
- Confirmation of IMP compliance

7) Adjustment of infusion solution

Infusion solution will be checked and adjusted at least 3 times to correct electrolyte abnormalities based on the blood pressure, pulse rate, body weight, serum sodium

concentration, serum potassium concentration, urine volume, fluid intake, and other parameters measured before, and at 4 and 8 hours after start of IMP administration.

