Body weight	Before IMP administration on Day 1 (Screening values will be used if the values at screening are measured on Day 1 but not measured prior to the IMP administration on that day.)	Day after final IMP administration
Congestive symptoms (lower limb edema, jugular venous distension, hepatomegaly, pulmonary rales, cardiac third sound)	Screening	Day after final IMP administration
Pulmonary congestion, cardiothoracic ratio	Screening	Day after final IMP administration
Respiratory rate, paroxysmal nocturnal dyspnea, orthopnea	Screening	Day after final IMP administration
Subject-assessed dyspnea	Screening	Day after final IMP administration
NYHA classification	Screening	Day after final IMP administration

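### The bedside congestive signs, respiratory rate, orthopnea and paroxysmal nocturnal dyspnea have no scheduled predose reading on Day 1, so up to about a day of pre-drug change enters their change from baseline

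*Protocol*

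**What the plan says.** **Timing of the Day 1 reading.** Table 3.7-1 marks dyspnea and congestive symptoms with a diamond, which the key defines as "At a feasible time (on Day 1, at a feasible time after start of IMP administration". Section 3.7.1.2 agrees. Its predose list (item 1) has body weight, chest x-ray, vital signs, ECG, laboratory tests and biomarkers, but none of the bedside signs. They come under item 6, "At a feasible time after start of IMP administration", as "Dyspnea (respiratory rate, paroxysmal nocturnal dyspnea, orthopnea, and subject-assessed dyspnea" and "Congestive symptoms (lower limb edema, hepatomegaly, jugular venous distension, pulmonary rales, and cardiac third sound".

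**Baseline.** SAP Table 3.4-1 lists "Congestive symptoms (lower limb edema, jugular venous distension, hepatomegaly, pulmonary rales, cardiac third sound" with Screening as baseline, and does the same for respiratory rate, orthopnea and paroxysmal nocturnal dyspnea. For body weight and vital signs the baseline is predose on Day 1, with the screening value allowed only when it was taken on Day 1.

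**The gap.** Section 3.7.1.1 lets screening run from Day -1 to predose on Day 1. Injectable loop diuretic is required at entry (Section 3.4.2) and continues through treatment (Section 3.1).

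**Use.** SAP 8.3.2 and 8.3.3 define resolution as a symptom present at baseline that has gone after the drug is given. They summarise resolution rates with exact 95% confidence intervals, and mean changes in jugular venous distension, hepatomegaly and respiratory rate with t-based intervals.

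**The concern.** The baseline for these items can precede the first dose by up to about a day, while the patient is already on injectable diuretic. A sign that clears in that interval is counted as having resolved after OPC-61815. Within one subject, weight change and symptom change can cover different periods although they are reported side by side. The trial has no control arm in which the same pre-dose drift would appear, and the SAP plans no sensitivity analysis for the gap. At stake is the accuracy of a set of descriptive rates and mean changes. No hypothesis test or decision rule depends on them.

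**Working it through.** **The plan's own figure.** The only design calculation is the chance of seeing at least one adverse event in 40 subjects: 1 − 0.95^40 = 87.1% and 1 − 0.96^40 = 80.5%, against the stated 87% and 80%. It reproduces, and nothing here depends on it.

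**Is there any predose reading on Day 1?** Only when the screening examination itself is done on Day 1. Footnote e of Table 3.7-1, under which "the measurements do not have to be repeated at predose on Day 1", covers local sodium and potassium, body weight, chest x-ray and vital signs. These have a scheduled predose reading that can be waived. The bedside signs, respiratory rate, orthopnea and paroxysmal nocturnal dyspnea have none to waive.

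**Share of the observation time that is pre-drug.** Let L be the time from screening to first dose and k the number of daily doses. The final reading is the day after the last dose, so the time from first dose to final reading is about 24k hours. Share = L / (L + 24k).

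| L | k = 1 | k = 2 | k = 3 | k = 5 |
|---|---|---|---|---|
| 24 h | 50% | 33% | 25% | 17% |
| 12 h | 33% | 20% | 14% | 9% |
| 6 h | 20% | 11% | 8% | 5% |
| 0 h | 0% | 0% | 0% | 0% |

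Short courses are part of the plan: Section 3.2.3 lets treatment end early once all congestive symptoms have resolved. The shares describe time and say nothing directly about effect.

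**Illustrated size for a resolution rate.** Let b be the share of signs present at screening that are gone before the first dose and stay gone, and r the resolution rate from a true predose baseline. Reported rate = 1 − (1 − b)(1 − r), so the excess is b(1 − r). The documents give neither b nor r; both are assumed.

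| b | r = 30% | r = 50% | r = 70% |
|---|---|---|---|
| 2% | +1.4 points | +1.0 | +0.6 |
| 5% | +3.5 | +2.5 | +1.5 |
| 10% | +7.0 | +5.0 | +3.0 |

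**The only background figure in the documents.** Protocol 1.2.3 reports a weight change of −0.45 kg over 7 days on placebo, in patients with volume overload despite conventional diuretics, against −1.54 kg on tolvaptan. If linear, that is 0.45/7 = 0.064 kg per day, or 0.064/1.54 = 4% of the tolvaptan change per day. It concerns weight, not bedside signs, so it is context only, but it suggests a small daily drift.

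**The case against.** The case for leaving the plan alone has real substance.

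- **These rates are not the whole efficacy description.** A reader might infer that, with no control arm, they are. Body weight has a predose Day 1 baseline and its own 95% confidence interval (SAP 8.3.1), and the rationale in Protocol 3.2.2 calls it the primary efficacy endpoint. SAP Section 6 sets no primary or secondary outcome variables. This objection stands.
- **The dose decision.** A reader might infer that pre-dose improvement would count at the Day 2 escalation decision and hold a subject at 8 mg. The documents do not establish this. The relevant branch of criterion 1 reads "Body weight did not decrease as compared with predose on Day 1 with no improvement in congestive symptoms" and names no reference time for the symptoms. Its rationale refers to the previous day for weight, which would be Day 1, when a post-start reading exists. The other branch asks only whether a symptom is present. What remains is unclear wording.
- **A predose check exists.** Eligibility is confirmed before dosing on Day 1 (Table 3.7-1 and Section 3.7.1.2, item 3), and inclusion criterion 2 requires at least one of three signs of volume overload. A subject who had lost all three should not be dosed. This limits the bias, but it gives no graded baseline and does not cover each sign.
- **A full day is the upper end.** Section 3.7.1.1.2 provides for less than 24 hours between consent and dosing, and its 24-hour urine collection does not fix when the signs are examined. This stands; hence the range of L above.
- **Background improvement remains anyway.** Loop diuretic continues during treatment and there is no control arm, so a predose baseline removes only the pre-dose part. This also stands.

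**Conclusion.** The point holds as a baseline-timing weakness in descriptive endpoints. For the five bedside signs, respiratory rate, orthopnea and paroxysmal nocturnal dyspnea, change from baseline can include up to about a day of pre-drug time: at most 17% of the interval for five doses and 50% for one, falling to near zero when screening is done on Day 1. The effect on the rates cannot be derived from the documents. It is an excess of 1 to 5 points if 2% to 10% of signs resolve before dosing and the true rate is 50%, or 0.6 to 7 points over true rates of 30% to 70%. The direction also rests on assuming that signs improve rather than worsen in the gap. The bias is probably modest.

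It would go too far to say that correcting the baseline isolates the drug's effect; on-treatment background improvement stays inseparable from OPC-61815 in this design. No effect on dose escalation is claimed.

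**What to change.** - **Protocol Table 3.7-1 and Section 3.7.1.2:** move the Day 1 reading of the five congestive signs, respiratory rate, orthopnea and paroxysmal nocturnal dyspnea to the predose list. Extend footnote e so that no repeat is needed when the screening reading was taken on Day 1. Leave the seven-level subject-assessed dyspnea rating after the dose.
- **SAP Table 3.4-1:** set the baseline for these items to the predose Day 1 reading, using the screening value when that was taken on Day 1, as already done for body weight and vital signs.
- **If the data are already collected:** report the distribution of the screening-to-first-dose interval and repeat the resolution and change summaries in subjects screened on Day 1.
- **Separately:** reconcile Day 2 escalation criterion 1 with its rationale in Section 3.2.2, so that the reference time for symptom improvement is stated.

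**Cost.** The change is one of wording and adds no assessment; one bedside examination moves to before the infusion. What is lost is the untimed post-start Day 1 reading in the shift tables. Day 2 then gives the first on-treatment value. The sample size and its stated probabilities do not change.
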